4.8.3.3 Exploratory Analyses

Other Efficacy Outcomes in Pre-specified Subpopulations of Asthma

Three secondary endpoints of change from baseline in the mean ACQ-6 score, the overall AQLQ(S)+12 score, and total rescue medication use at Week 52 will be analyzed by following pre-specified subpopulations of asthma: 1) eosinophilic and non-eosinophilic;

2) Th2 high/low (Corren et al, 2011); 3) FE_{NO} high/low; 4) periostin high/low; 5) current post-BD FEV_1 reversibility; and 6) allergic and non-allergic.

Effect on Efficacy Outcomes Through the Safety Follow-up Period

Reduction in AER will be evaluated at Week 64. Change from baseline in lung function as measured by pre- and post-BD FEV_1 and FVC, in asthma symptoms (daytime and nighttime symptom frequency and severity, activity avoidance and limitation, asthma-related stress and fatigue as well as rescue medication use) as measured by the Asthma Daily Diary, asthma control as measured by the ACQ-6, and HRQoL as measured by the AQLQ(S) +12 will be evaluated.

Healthcare Resource Utilization

Healthcare resource utilization will be evaluated by the number and proportion of subjects who use a healthcare resource by Week 64.

WPAI+CIQ

The WPAI+CIQ provides employment and academic status as well as 4 types of scores: absenteeism (work/class time missed), presenteeism (impairment at work/in class or reduced on-the-job/classroom effectiveness), productivity loss (overall work/classroom impairment/absenteeism plus presenteeism), and activity impairment for regular activities. Absenteeism, presenteeism, productivity loss, and activity impairment for each treatment group will be evaluated and will be presented as the proportion of impairment.

Biomarkers

The relationship between changes in biomarkers and asthma, Th2 inflammation, and the TSLP pathway may be explored. Baseline serum blood biomarkers and FE_{NO} results will be explored to identify predictive biomarkers of MEDI9929 response. Three secondary endpoints of change from baseline in the mean ACQ-6 score, the overall AQLQ(S)+12 score, and total rescue medication use at Week 52 may be analyzed by TSLP-related biomarkers.

Biomarkers include cytokines, chemokines and inflammatory mediators associated with asthma and the TSLP pathway. Intracellular cytokines in T cells by flow cytometry following *ex vivo* stimulation by phorbol myristate acetate may also be evaluated.

DNA will be extracted and polymorphisms associated with asthma, TSLP or MEDI9929 response may be analyzed (optional for subjects).

These data will be reported separately from the clinical study report.

4.8.3.4 Subgroup Analyses

The subgroup analyses listed below, based on populations of interest, will be conducted at Week 52 on reduction in AER, change from baseline in FEV₁, and change from baseline in overall symptom score. The baseline variables listed below may also be assessed as covariates in a sensitivity analysis of the primary statistical model, if not already included, to assess any possible influence on the endpoints.

- 1. Peripheral blood eosinophil count $\geq 250 \text{ versus} < 250 \text{ cells/}\mu\text{L}$
- 2. Th2 status: high: IgE > 100 IU/mL and blood eosinophil count \geq 140 cells/ μ L versus low: IgE \leq 100 IU/mL or blood eosinophil count < 140 cells/ μ L
- 3. FE_{NO:} high versus low determined by median
- 4. Serum periostin level: high versus low determined by median level
- 5. Current post-BD FEV₁ reversibility defined as a post-BD change in FEV₁ of ≥ 12% and ≥ 200 mL demonstrated at one of the screening visits (Visit 1 [Week -5], Visit 2 [Week -4], or Visit 3 [Week -1])
- 6. Allergic versus non-allergic
- 7. Study sites: non-Japanese versus Japanese
- 8. ICS dose level: medium versus high

In addition to the 250 cells/ μ L cutoff for blood eosinophils, blood eosinophil counts as a continuous variable will be explored to differentiate between a responder and non-responder population. One blood eosinophil count cutoff may be selected for the Phase 3 eligibility criterion based on the treatment effect. Additional analyses on secondary endpoints and safety may be conducted based on the selected cutoff.

Analyses of the following subgroup populations of interest may also be conducted:

- 1. Gender: male versus female
- 2. Race: White versus non-White
- 3. Maintenance OCS use at screening: presence versus absence
- 4. $FE_{NO} \ge 24$ ppb versus < 24 ppb (Hanania et al, 2013; Dweik et al, 2011)
- 5. Number of prior asthma exacerbations in the past year: 2 versus ≥ 3
- 6. Geographical region: North America/Western EU versus rest of world

Safety data will not be analyzed separately by subgroup.

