4.8.2 Sample Size and Power Calculations

Sample size calculations have been performed for the primary endpoint of annualized AER, based on the negative binomial distribution (Keene et al, 2007). Approximately 552 subjects will be randomized in the study, with approximately 85% of the total number of subjects designated as non-Japanese subjects (ie, subjects enrolled at sites outside of Japan) and approximately 15% of the total number of subjects designated as Japanese subjects (ie, subjects enrolled at sites in Japan). The total enrollment may exceed 552 subjects depending on whether additional non-Japanese subjects are enrolled to mitigate for slow enrollment in Japan, and to accommodate subjects in screening/run-in when the different strata are closed to enrollment.

Subjects will be randomized in a 1:1:1:1 ratio to receive one of 3 dose levels of SC MEDI9929 (280 mg Q2W, 210 mg Q4W, or 70 mg Q4W) or placebo Q2W for 52 weeks. Prior to randomization, subjects will be stratified by study site (non-Japanese and Japanese) and then by blood eosinophil count (\geq or< 250 cells/ μ L) and ICS dose level (medium or high). Subjects taking maintenance OCS will be automatically assigned to the high-dose ICS strata. At least 50% of the total subjects will be enrolled in the high blood eosinophil stratum (\geq 250 cells/ μ L), and at least 40% of the subjects in each blood eosinophil stratum will be receiving high-dose ICS. Details on the 8 strata (4 strata for non-Japanese subjects and 4 identical strata for Japanese subjects) are included in Section 3.1.1.

The primary analysis will be based on the ITT population. The 3 primary comparisons are as follows: MEDI9929 280 mg Q2W versus placebo; MEDI9929 210 mg Q4W versus placebo; and MEDI9929 70 mg Q4W versus placebo. A total of 124 subjects per treatment group would be required to detect a 40% reduction in the annual AER for each MEDI9929 dose group compared to placebo group, assuming an AER of 0.7 in the placebo group, a two-sided significance level of 0.1, 80% power, and a dispersion parameter of 0.7 based on the negative binomial distribution. The AER of 0.7 in the placebo group was estimated based on internal and external studies with a similar subject population (before considering dropouts). The dispersion parameter of 0.7 was selected from the mepolizumab study in subjects with severe, eosinophilic asthma (Pavord et al. 2012). Sample size was increased to 138 per

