treatment group to accommodate a 10% loss of information due to dropouts. The minimal detectable difference is approximately 28% reduction in annual AER. Figure 4.8.2-1 provides power calculations based on varying sample sizes for a selected treatment effect of AER reduction of 40% and 50%. The minimum acceptable reduction in the annual AER of 40% for the study population was based upon an expected reduction of approximately 50% in a Th2-driven asthma population which appears to be achievable in competitors which target Th2 cytokines (eg, IL-13, IL-5) and a more modest reduction in a non-Th2 asthma population for which there are little data and no current competitors.

[figure not shown]

Figure 4.8.2-1 Power Calculations for an Annual Asthma Exacerbation Rate of 40 Percent or 50 Percent

AER = asthma exacerbation rate; AERR =asthma exacerbation rate reduction; yr = year Note: The sample sizes do not reflect the projected dropout rate.

It is generally recommended that Japanese subjects be included in studies to identify interethnic differences in the dose-response relationship early in clinical development. The target percentage of Japanese subjects for inclusion in this study is approximately 15% of the targeted enrollment of 552 subjects. A subgroup analysis of the non-Japanese subjects and Japanese subjects will be performed. Due to a small sample size, the subgroup analysis of the

Japanese subjects will not have sufficient power to detect differences with statistical significance.

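### A Phase 3 eosinophil cut-off may be chosen on the observed treatment effect; the effect read at that cut-off in the same subjects would be biased upward

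*Protocol*

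**What the plan says.** Protocol Section 4.8.3.4 lists the split at 250 cells/µL first among its subgroups. It adds that the count will also be explored as a continuous variable, to separate responders from non-responders. It then states: "One blood eosinophil count cutoff may be selected for the Phase 3 eligibility criterion based on the treatment effect". The next sentence is: "Additional analyses on secondary endpoints and safety may be conducted based on the selected cutoff". The section ends: "Safety data will not be analyzed separately by subgroup".

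Section 3.2.2 shows that 250 cells/µL was taken from the median count in earlier, similar populations, so it does not depend on this trial's results. Section 4.8.2 expects a reduction of about 50% in Th2-driven asthma and a smaller one in non-Th2 asthma. Section 1.5 says the results will inform the design of later studies.

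**The concern.** Each subgroup estimate is the true effect plus sampling error. A cut-off chosen because the effect above it looks strong is partly chosen for favourable error, and reading the effect there in the same subjects keeps that error in the estimate. The estimate below the cut-off tends to be pushed the other way, so a drug that works equally at all counts can appear to work mainly in high-eosinophil patients.

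That false pattern resembles what Section 4.8.2 already expects, so it could pass without question. At stake are the Phase 3 eligibility threshold and, if the estimate is carried forward, the assumed Phase 3 effect. Section 3.2.2 argues that the drug may work in both Th2 and non-Th2 disease, so a spurious threshold would matter.

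**Working it through.** **Inputs from Section 4.8.2.** The design is stated as "assuming an AER of 0.7 in the placebo group, a two-sided significance level of 0.1, 80% power, and a dispersion parameter of 0.7". Also: "A total of 124 subjects per treatment group would be required to detect a 40% reduction in the annual AER"; 138 after an allowance for 10% dropout; "The minimal detectable difference is approximately 28% reduction in annual AER". Allocation is 1:1:1:1 and treatment lasts 52 weeks.

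**The plan's own figures.**
- Variance term: 1/0.7 + 1/0.42 + 2 × 0.7 = 5.2095.
- n per arm = (1.645 + 0.842)² × 5.2095 / (ln 0.6)² = 6.183 × 5.2095 / 0.2609 = 123.4, so 124.
- Dropout: 124 / 0.9 = 137.8, so 138.
- Minimal detectable reduction: 1 − exp(−1.645 × √(5.2095/124)) = 28.6%, or 27.7% if the variance uses the detectable rate itself. The plan says about 28%.

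All three reproduce.

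**How noisy a subgroup is.** With about half of each arm above the cut-off (62 subjects), the standard error of the log rate ratio is √(5.2095/62) = 0.290. One standard error of favourable error turns a true 40% into 1 − 0.6 × exp(−0.290) = 55%.

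**Simulation.** There were 20,000 trials with 124 per arm, negative binomial counts, and a true 40% reduction at every eosinophil level. The candidate cut-offs and selection rules are assumptions, since the protocol gives none. Cells show the mean apparent reduction above / below the selected cut-off, in percent.

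| Comparison and candidate percentiles | Largest reduction above | Largest above-below contrast | Smallest p above |
|---|---|---|---|
| One dose, 7 cut-offs (20th to 80th) | 52.7 / 32.8 | 51.3 / 26.9 | 47.6 / 30.8 |
| One dose, 3 cut-offs (25, 50, 75) | 49.1 / 35.3 | 48.0 / 31.1 | 45.4 / 35.1 |
| One dose, 3 cut-offs (40, 50, 60) | 45.4 / 35.9 | 45.1 / 34.8 | 44.5 / 35.9 |
| Doses pooled, 7 cut-offs | 49.5 / 34.3 | 48.2 / 29.3 | 45.1 / 32.7 |
| Doses pooled, 3 cut-offs (40, 50, 60) | 43.9 / 36.5 | 43.6 / 35.6 | 43.1 / 36.6 |

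- Fixed median cut-off, one dose: 40.1%.
- Selected cut-off applied to fresh outcomes, one dose: 39.9% to 40.1%. The bias therefore comes from reusing the same data.
- One dose, 7 cut-offs: the upper group looks at least 10 points better than the lower in 62% to 71% of trials, although no difference exists.
- No true effect, one dose, 7 cut-offs: the apparent reduction is 17% to 19%, and a favourable nominal p < 0.10 occurs in 11% to 14% of trials against 5% expected.

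**Second simulation.** This used 138 per arm and assumed lognormal counts (median 250, log-SD 0.8). Median apparent reductions for one dose / doses pooled:
- Best of 8 cut-offs from 150 to 500 on the lowest rate ratio: 52% / 49%.
- The same 8 on the test statistic: 47% / 44%.
- Three cut-offs (200, 250, 300): 42% to 45% across rules and comparisons.

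The 500 cut-off is chosen in about 24% of trials on the lowest rate ratio, but only 2% to 3% on the test statistic.

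**A threshold rule.** Taking the lowest cut-off with an observed reduction of at least 50% succeeds in 30% to 52% of trials. The mean apparent reduction is then 54% to 57%. These figures are conditional on the rule being met, so they are kept out of the main range.

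**Carry-over to a secondary endpoint.** A true difference of 0.30 SD is estimated as 0.30 if the endpoint is uncorrelated with exacerbations, 0.32 at a correlation of magnitude 0.16, and 0.34 at 0.32.

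**The case against.** The strongest reply is that this is exploratory Phase 2 work. Finding a likely responder population is a declared aim (Section 3.2.3), and the wording is permissive throughout. Section 4.8.1 leaves further statistical detail to an SAP that is not at hand and may contain a correction. The count is already to be explored continuously, and the 250 cells/µL results will be reported regardless. Phase 3 would re-estimate the effect in new subjects.

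Most of this stands and limits the point. It does not remove it, because the protocol itself names the observed effect as the basis of selection and allows reuse in the same subjects. The point does not rest on a correction being absent.

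A reader might infer more than the documents support:
- **That the best-looking cut-off will be taken and reused.** The text says only that this may happen. A selection based on the effect could also mean reading a threshold from a fitted curve.
- **That the inflation is about 12 points and selection favours small extreme groups.** Both depend on choosing the lowest raw rate ratio among many cut-offs; other rules give less and rarely pick the extreme.
- **That secondary endpoints are equally inflated.** The carry-over figures show they are not.
- **That the trial's main result is compromised.** The step-down test in the ITT population does not use the selected cut-off.

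The safety sentences could be read as a general rule with an optional exception, but the section does not say so.

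**Conclusion.** The point holds in limited form. If the effect is read at a cut-off selected on that effect, it is biased upward under every rule tried. With a true uniform 40% reduction, the apparent reduction is about 42% to 53% above the selected cut-off and about 27% to 37% below it, against an unbiased 40% at 250 cells/µL. The range rests on the Section 4.8.2 design values and on assumed candidate cut-offs and rules. The exacerbation estimate is inflated directly if exacerbations drive the selection.

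The consequence is an optimistic subgroup effect and possibly an unwarranted eligibility limit for Phase 3. There is no error in the confirmatory analysis. This is worth correcting but does not threaten the trial. The conflict between the two safety sentences is a separate, minor matter of wording.

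**What to change.** 1. Base any cut-off selection on a negative binomial model with a treatment by continuous (log) eosinophil count interaction, fitted to all subjects. Fix the selecting endpoint, the dose comparison and the selection rule before unblinding. The first planned unblinded efficacy look is the Week 28 interim analysis in Section 4.8.7.
2. Report the rate ratios above and below the selected cut-off with a bootstrap that repeats the selection in every resample, giving optimism-corrected estimates and intervals. Place them beside the prespecified 250 cells/µL results.
3. Label all other analyses at the selected cut-off as exploratory.
4. Reconcile "Additional analyses on secondary endpoints and safety may be conducted based on the selected cutoff" with "Safety data will not be analyzed separately by subgroup", stating whether safety by the selected cut-off is an intended exception.

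The cost is some wording and a little programming. No change to enrolment or data collection is needed. The reported effect above the selected cut-off will be less favourable.

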4.8.4 Patient-reported Outcomes

Asthma Control Questionnaire-6

Asthma control will be evaluated by ACQ-6. The change from baseline in the mean ACQ-6 score will be analyzed. The proportion of subjects with change from baseline in the mean ACQ-6 score ≥ 0.5 during the study and the proportion of subjects who are well controlled (mean ACQ-6 score of ≤ 0.75), partially controlled (0.75 < mean ACQ-6 score ≤ 1.5), and uncontrolled (mean ACQ-6 score ≥ 1.5) will be compared between the individual MEDI9929 group and placebo group using the Fisher's exact test. A stratified log-rank test will be conducted to compare the time to first asthma control defined as a reduction from baseline in the mean ACQ-6 score ≥ 0.5 is first observed and the time to first partially control (0.75 < mean ACQ-6 score ≤ 1.5) and well controlled (mean ACQ-6 score of ≤ 0.75).

Asthma Daily Diary

Each item of the Asthma Daily Diary will be summarized showing change over time compared to baseline scores. Baseline will be defined as the 14-day period prior to dosing on Day 1 (ie, Day -15 to Day -1). Asthma Daily Diary data will be summarized as biweekly (14 day) means post dosing on Day 1. The change from baseline in the following endpoints will be analyzed:

- The mean symptom scores for daytime severity, daytime frequency, nighttime severity, and overall symptom score, where overall symptom score is the average of scores of daytime severity, daytime frequency, and nighttime severity
- The mean scores for the activity limitation questions
- Number of times rescue medication is used: daytime use, nighttime use, total rescue medication use (daytime + nighttime)
- The proportion of nights without nocturnal awakening and the proportion of nights without asthma-related nocturnal awakening (no awakening or wakening without rescue medication use)

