4.3.2.2 Asthma Control Questionnaire-6

The ACQ is a patient-reported questionnaire assessing asthma symptoms (ie, night-time waking, symptoms on waking, activity limitation, shortness of breath, wheezing) and daily rescue bronchodilator use and FEV₁ (Juniper et al, Oct 1999). The ACQ-6 is a shortened version of the ACQ that omits the FEV₁ measurement from the original ACQ score. Questions are weighted equally and scored from 0 (totally controlled) to 6 (severely uncontrolled). The mean ACQ score is the mean of the responses. Mean scores of \leq 0.75 indicate well-controlled asthma, scores between 0.75 and \leq 1.5 indicate partly-controlled asthma, and a score > 1.5 indicates uncontrolled asthma (Juniper et al, 2006). Individual changes of at least 0.5 are considered to be clinically meaningful (Juniper et al, 2005).

The study center staff will provide initial training on the ePRO device at Visit 1 (Week -5) in order for the subject to complete the screening ACQ-6 at the study center. The ePRO device will remain at the study center until Visit 2 (Week -4).

At Visit 2 (Week -4), study center staff will provide training as described in Section 4.3.2 and will give the subject the ePRO device to take home. The subject will complete the ACQ-6 weekly during the Screening/Run-in period. The Visit 2 (Week -4), Visit 3 (Week -1), and Visit 4 (Week 0, Day 1) ACQ-6 will be completed at the study site on the ePRO device. Subjects will be prompted to complete the ACQ-6 at Week -3 and Week -2 at home on the ePRO device. Once randomized, subjects will be prompted to complete the ACQ-6 every 2 weeks at home on the ePRO device through Week 64.

Subjects must have an ACQ-6 score of ≥ 1.5 twice during screening. The first time must be at Visit 1 (Week -5). If the ACQ-6 score is not ≥ 1.5 at Visit 1 (Week -5), then the subject should not continue in the study (screen failure). The second time the subject must have an ACQ-6 score of ≥ 1.5 may be at either Week -2 (at home on the electronic patient-reported outcome [ePRO] device) or at Visit 3 (Week -1).

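### Section 4.8.4 gives the ACQ-6 change rule no direction, puts a score of 1.5 in two control categories, and lets the partial-control event miss subjects who improve past its band

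*Protocol*

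**What the plan says.** Protocol section 4.3.2.2 describes the instrument. Items are "scored from 0 (totally controlled) to 6 (severely uncontrolled", and "The mean ACQ score is the mean of the responses". Asthma is well controlled at 0.75 or less and partly controlled above 0.75 up to 1.5, "and a score > 1.5 indicates uncontrolled asthma". On change, the section says "Individual changes of at least 0.5 are considered to be clinically meaningful", without a direction.

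Section 4.8.4 then sets the ACQ-6 analyses:

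- Fisher's exact test compares "The proportion of subjects with change from baseline in the mean ACQ-6 score ≥ 0.5 during the study".
- The same test compares the control categories: well controlled (0.75 or less), partially controlled (above 0.75 and up to 1.5), and "uncontrolled (mean ACQ-6 score ≥ 1.5) will be compared between the individual MEDI9929 group and placebo group".
- A stratified log-rank test compares "time to first asthma control defined as a reduction from baseline in the mean ACQ-6 score ≥ 0.5", and also time to first partial control, defined by the band above 0.75 and up to 1.5, and to well controlled, defined as 0.75 or less.

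**The concern.** The protocol itself fixes these rules, and they feed between-arm tests on a patient-reported outcome in a dose-ranging trial. Three of them go wrong if programmed as written.

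1. A positive change on this scale is deterioration. Taken literally, the compared proportion falls as a dose works better, and it points the opposite way from the time-to-event rule in the following sentence.
2. A subject scoring exactly 1.5 is counted in two categories. The three percentages can then add to more than 100%, and the uncontrolled share is larger than under the definition in section 4.3.2.2.
3. The partial-control event has a lower bound. A subject who improves past the band between two assessments is treated for a time, or for good, like one who has not improved, which works against an effective dose in the log-rank test.

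**Working it through.** The protocol states no sample size, power or alpha that depends on these rules, so there is no figure to reproduce. The check applies the definitions to the scores that can occur.

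**Inputs.** The scale direction, the scoring as a mean of equally weighted items and the ACQ-6 interval of every 2 weeks after randomization come from section 4.3.2.2. The category cut-points and events come from section 4.8.4. The entry threshold of at least 1.5 on two screening occasions is inclusion criterion 9 in section 4.1.2. Baseline, the last valid assessment before first dose, is defined in section 4.8.1.

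**Direction.** Take a baseline of 2.5.

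- Change of at least +0.5, as written: score ≥ 2.5 + 0.5 = 3.0, which is worsening.
- Reduction of at least 0.5, as in the next sentence: score ≤ 2.5 − 0.5 = 2.0, which is improvement.
- Absolute change of at least 0.5: score ≤ 2.0 or ≥ 3.0, which pools the two.

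The size can only be illustrated under assumptions. Let change be normal with mean μ and SD 1. The proportion meeting the literal rule is 1 − Φ(0.5 − μ), and the proportion improving by at least 0.5 is Φ(−0.5 − μ).

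| Assumed μ | Literal rule | Improved by ≥ 0.5 |
|---|---|---|
| 0 | 1 − Φ(0.5) = 31% | Φ(−0.5) = 31% |
| −1.0 | 1 − Φ(1.5) = 6.7% | Φ(0.5) = 69% |

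As average improvement grows, the two proportions move in opposite directions.

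**Overlap.** A complete ACQ-6 is the mean of six items scored 0 to 6, so scores lie on k/6 for k = 0 to 36, which is 37 values. Under section 4.8.4, 36 of them fall in one category and one, 9/6 = 1.5, falls in two. With uncontrolled set above 1.5, as in section 4.3.2.2, all 37 fall in exactly one. Nothing needs to be assumed for this.

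How often 1.5 occurs does need an assumption. With normal scores of mean m and SD 1, the share at 1.5 is about φ(1.5 − m) × 1/6:

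- m = 1.3: 0.391/6 = 6.5%
- m = 1.5: 0.399/6 = 6.6%
- m = 2.0: 0.352/6 = 5.9%

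That is about 6% to 7%. The three category percentages would add to 100% plus this share.

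**Partial-control event.** Four sequences of successive scores, showing which score gives the event:

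| Scores | Band as written | First score ≤ 1.5 | First score ≤ 0.75 |
|---|---|---|---|
| 2.5, 1.33, 0.67 | second | second | third |
| 2.5, 2.0, 0.67, 0.5 | none | third | third |
| 2.5, 2.0, 0.67, 1.33 | fourth | third | third |
| 1.5, 1.33 | first | first | none |

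The second sequence is censored for partial control although the subject is well controlled. The third has its event late. The fourth shows a separate difficulty: criterion 9 constrains screening scores, not baseline, so a subject may already be at or below 1.5 at time zero. Removing the lower bound alone would not cure that.

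**The case against.** A reader might infer that the protocol defines worsening as response. It does not. Section 4.8.4 never calls the ACQ-6 rule a responder rule. Section 4.3.2.2 uses the same unsigned wording for a meaningful change, the next sentence of section 4.8.4 says reduction, and section 4.8.4.1 says improvement for the AQLQ(S)+12. In context this is a missing sign. That stands as to intent, but the sentence still specifies a test whose literal reading gives the wrong proportion.

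A reader might also infer that the best improvers can never have the partial-control event. That is too strong. ACQ-6 continues every 2 weeks through Week 64, so a later score in the band supplies the event. Only subjects who skip the band and never score in it afterwards are lost. The accompanying time to well controlled captures all who reach 0.75 or less. The wording could also join partial and well controlled into one event, in which case this part disappears. Two separately defined states is the more natural reading, and the text does not say otherwise.

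Criterion 9 admits scores of exactly 1.5 at screening, but says little about how often 1.5 occurs after baseline. The 6% to 7% therefore rests wholly on the assumed mean and SD.

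The reach is limited. The ACQ-6 endpoint in section 2.2.2 is change from baseline at Week 52; these proportions and times supplement it. Section 4.8.1 makes the p-values nominal and leaves further detail to an SAP that was not available here. A later document may settle the wording, but the overlap contradicts section 4.3.2.2 within the protocol itself.

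**Conclusion.** The point holds as a low-severity correction. The missing direction and the double-counted 1.5 are wrong as written and follow from the protocol's text alone. The partial-control flaw holds if partial and well controlled are separate events. It misses or delays the event for subjects who pass from above 1.5 directly to 0.75 or below, and censors them only if no later score falls in the band. No magnitude can be given for that part from the document. The percentages for the other two are illustrations under assumed means with SD 1.

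A broader reading, that the trial's efficacy conclusions are at risk, is not supported. The primary endpoint, the alpha, the sample size and the ACQ-6 mean-change analysis do not use these rules.

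**What to change.** Make three wording changes in section 4.8.4:

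1. State the compared proportion as subjects with a reduction from baseline in mean ACQ-6 of at least 0.5 (change ≤ −0.5).
2. Define uncontrolled as a mean ACQ-6 above 1.5, matching section 4.3.2.2, so that the three categories are mutually exclusive.
3. Replace time to first partial control with time to at least partial control: the first post-baseline score of 1.5 or less, among subjects with baseline above 1.5. Keep time to well controlled (0.75 or less) alongside it.

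The baseline restriction in the third change prevents events at time zero. It removes subjects with baseline of 1.5 or less from that one analysis. Because it conditions on a pre-dose value, it does not select on response to treatment.

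No new data, visits or subjects are needed. The changes should be made before unblinding, which here means before the interim analysis, since section 4.8.7 has that analysis use all data available at the time.
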